16.1.1.2. Sensitivity Analyses of PANSS Total Score

Patterns of the observed data in the exploratory endpoint will be examined through graphical tools based on the reason and the timing of study treatment withdrawal.

Mean change from Baseline in PANSS total score at each time point will be plotted by the reason of early discontinuation (adverse event [separately by COVID-19 relatedness], lack of efficacy, lost to follow-up, withdrawal by subject, non-compliance with study drug, protocol deviation, death [separately by COVID-19 relatedness], pregnancy, other [separately by COVID-19 relatedness]) and for completers, separately for each treatment group. Similar reasons may be combined, depending on the number of subjects who

Document: CCI

Author: PPD

Version Number: 0.6

Version Date: 30JAN2023

Template No.: CS_TP_BS016 Revision 6

Reference: CS_WI_BS005

Effective Date: 02Dec2019

discontinued under each reason. Reason pooling will be determined at the Blinded Data Review meeting prior to database lock and treatment unblinding.

Mean change from baseline in PANSS total score at each time point will also be plotted by the timing of early discontinuation (Week 1 terminators, Week 4 terminators, Week 8 terminators, Week 16 terminators, Week 24 terminators, Week 32 terminators, Week 40 terminators, Week 48 terminators, Week 52 terminators) and for completers, separately for each treatment group.

- Week 1 terminators: subjects who discontinue after Visit 2 but before or on Visit 3;
- Week 4 terminators: subjects who discontinue after Visit 3 but before or on Visit 5;
- Week 8 terminators: subjects who discontinue after Visit 5 but before or on Visit 6;
- Week 16 terminators: subjects who discontinue after Visit 6 but before or on Visit 8;
- Week 24 terminators: subjects who discontinue after Visit 8 but before or on Visit 10;
- Week 32 terminators: subjects who discontinue after Visit 10 but before or on Visit 12;
- Week 40 terminators: subjects who discontinue after Visit 12 but before or on Visit 14;
- Week 48 terminators: subjects who discontinue after Visit 14 but before or on Visit 16;
- Week 52 terminators: subjects who discontinue after Visit 16 but before Visit 17 (the EOT visit).

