15. STATISTICS

15.1. Sample Size

A total of 300 subjects are expected to be enrolled from approximately 50 global sites, including the US and Europe. Subjects will be assigned randomly to receive SEP-363856 or active comparator in an allocation ratio of 2:1. The determination of sample size was based upon clinical considerations. The sample size of 300 subjects will provide approximately 80 subjects who are expected to complete 1 year of treatment with SEP-363856 to support sufficient long-term safety data on SEP-363856.

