In case the model above fails to converge, a spatial exponential covariance structure and a spatial power covariance structure will be assumed sequentially. The first covariance structure to yield convergence will be used in the analysis. These analyses will be based on the observed data only. Missing data will not be imputed.

Sensitivity analyses may be conducted to assess the impact of missing data on the PANSS total score and CGI-S score analysis results by deviating away from the MAR assumption; however, all efficacy analyses are exploratory in this safety study.

Relapse

Relapse will be identified programmatically and manual data review using the pre-defined criteria (specified below). The rate of relapse will be calculated as the proportion of subjects with

a relapse in the 52-week period out of the efficacy population, along with the 95% confidence interval. The time-to-relapse will be summarized descriptively and will also be presented by a Kaplan-Meier plot, with log rank test statistic.

Relapse will be defined as the earliest occurrence of any of the following:

- Worsening of > 30% PANSS total score from Baseline (Day 1) and a CGI-S score > 3.
- Hospitalization for worsening of psychosis.
- Emergence of suicidality, homicidality and/or risk of harm to self or others.
- Discontinuation from the study due to exacerbation of the underlying illness of schizophrenia.

The frequency of hospitalization due to relapse will be summarized descriptively by treatment.

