2.2.4. CCI

3. STUDY DESIGN

3.1. GENERAL DESCRIPTION

This is a 52-week, multicenter, randomized, double-blind, parallel-group, flexible-dose study designed to evaluate the long-term safety and tolerability of SEP-363856 (50 to 100 mg/day) in clinically stable adults with schizophrenia. This study is projected to randomize approximately 300 subjects to two treatment groups (SEP-363856 50 to 100 mg/day or Quetiapine XR 400 to 800 mg/day) in a 2:1 ratio.

Study drug will be taken at the same time each evening at bedtime and should be taken without food or with a light meal.

The study will consist of three periods: Screening/Washout (up to 21 days), Treatment (52 weeks) and a Follow-up Visit (7 days after the last study drug dose).

A study schematic is presented in Figure 1.

Document: CCI

Author: PPD

[figure not shown]
Version Number: 0.6

Version Date: 30JAN2023

Template No.: CS_TP_BS016 Revision 6

Reference: CS_WI_BS005

Effective Date: 02Dec2019

Figure 1: Study schematic

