3.2. METHOD OF ASSIGNING SUBJECTS TO TREATMENT GROUPS

The randomization schedule is generated by a non-study biostatistician.

The randomization is stratified by country and the randomization schedule is based on permuted blocks.

Once a subject is deemed eligible to be randomized at Day 1, an interactive web response system (IWRS) will perform treatment assignment. Subjects will be randomized to one of the following treatment groups in a 2:1 ratio:

- Flexibly dosed SEP-363856 (50, 75, or 100 mg/day) for 52 weeks
- Flexibly dosed Quetiapine XR (400, 600, or 800 mg/day) for 52 weeks

Once a randomization number has been assigned, it cannot be reused.

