6.6. STATISTICAL TESTS

The default significance level will be 5%; confidence intervals (CIs) will be 95%; and all p-values will be two-sided, unless otherwise specified in the description of the analyses or the outputs.

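### The SAP's sensitivity analyses for PANSS and CGI-S are plots only, and no visible text specifies a formal departure from MAR for the Week 52 MMRM

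*SAP*

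**What the plan says.** SAP 16.1.1.1 analyses change in PANSS total score with an MMRM over nine post-baseline visits under MAR. It reports the Week 52 difference from quetiapine XR, together with arm means and within-arm effect sizes. SAP 7.3 confirms that this model imputes nothing.

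SAP 16.1.1.2 is the section headed as sensitivity analyses. It states: "Patterns of the observed data in the exploratory endpoint will be examined through graphical tools". Two sets of plots follow, one by reason for leaving and one by time of leaving. SAP 16.2.1 sends CGI-S to the same section.

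SAP 16.1.1.3 adds supplementary analyses. Both endpoints get an ANCOVA at each visit and at the LOCF endpoint, an MMRM on completers and an MMRM on the per protocol population. PANSS total also gets multiple imputation of missing items, for partly completed assessments only.

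Protocol 15.3.5 had provided that "Sensitivity analyses may be conducted to assess the impact of missing data on the PANSS total score and CGI-S score analysis results" through departures from MAR. The same sentence calls all efficacy analyses exploratory. SAP 3.7, which lists changes from the protocol, does not say that this option was left unused.

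On expected retention, Protocol 15.1 says: "The sample size of 300 subjects will provide approximately 80 subjects who are expected to complete 1 year of treatment with SEP-363856". It gives no dropout rate, only that "The determination of sample size was based upon clinical considerations".

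**The concern.** A sensitivity analysis should re-estimate the result under a different assumption about the unobserved data. Plots of observed means do not do that, although they can suggest where MAR is doubtful.

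The assumption carries weight here for two reasons. First, many subjects are expected to leave, and off-drug data cannot fill the gap: Protocol 13.1 takes subjects who stop study drug out of the study, and SAP 6.5 excludes data from more than 9 days after the last dose. Second, leaving is partly tied to outcome. Lack of efficacy is a listed reason (Protocol 13.1). Psychotropic treatment for an exacerbation outside the permitted list leads to discontinuation (Protocol 10.3.2), and so does Type 4 or 5 suicidal ideation (Protocol 11.5.10).

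At stake is the reading of long-term effectiveness. The Week 52 arm means and their difference would be reported with no measure of how much they owe to the assumption that leavers go on to evolve like those who stay.

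**Working it through.** **1. Retention implied by the plan.** Inputs: "This study is projected to randomize approximately 300 subjects to two treatment groups" (SAP 3.1), "Subjects will be randomized to one of the following treatment groups in a 2:1 ratio" (SAP 3.2), and a total that "will provide approximately 80 subjects who are expected to complete 1 year of treatment with SEP-363856" (Protocol 15.1).
- SEP-363856 arm: 300 × 2/3 = 200. Quetiapine XR arm: 300 × 1/3 = 100.
- Completion: 80/200 = 40%. Non-completion: 1 − 80/200 = 60%. Check: 80/(1 − 0.60) = 200.
- If approximately 80 means 75 to 90: 1 − 75/200 = 62.5% and 1 − 90/200 = 55%.

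The 40% is back-calculated. No retention rate is stated, so the 80 cannot be reproduced independently. Quetiapine XR dropout is not stated at all.

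**2. Non-completion is not the share of data missing.** Assume 40% retention at Week 52 and three dropout shapes for the proportion S(t) still in the study at week t. Average over the MMRM visits (Weeks 1, 4, 8, 16, 24, 32, 40, 48, 52). SAP 6.4 maps an early termination (ET) score to the next visit at which that assessment is planned. If every leaver has such a score, missingness at a visit becomes 1 − S(previous visit).

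| Assumed S(t) | Mean missing, 9 visits | Mean missing, ET mapped | Week 52 missing, ET mapped |
|---|---|---|---|
| Linear: 1 − 0.6t/52 | 28.8% | 22.2% | 55.4% |
| Constant hazard: 0.4^(t/52) | 32.4% | 25.7% | 57.1% |
| Early-loaded: exp[ln 0.4 × (t/52)^0.5] | 41.8% | 35.1% | 58.5% |

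**3. Effect on the SEP-363856 mean.** If missing Week 52 values are worse than MAR predicts by δ, the arm mean moves by m × δ, where m is the fraction missing. The documents give no δ, so 5 points is an assumption.
- m = 0.60: 0.60 × 5 = 3.0 points (δ = 2 gives 1.2, δ = 8 gives 4.8).
- m from 0.55 to 0.625: 2.75 to about 3.1 points.
- ET scores mapped (m = 0.554 to 0.585): about 2.8 to 2.9 points.

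**4. Effect on the treatment difference.** With δ in SEP-363856 alone, the difference also moves by 3.0 points. With the same δ in both arms it moves by (0.60 − m_Q) × δ, where m_Q is the assumed quetiapine XR dropout. Positive values are unfavourable to SEP-363856.

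| m_Q | δ = 2 | δ = 5 | δ = 8 |
|---|---|---|---|
| 40% | +0.4 | +1.0 | +1.6 |
| 50% | +0.2 | +0.5 | +0.8 |
| 60% | 0 | 0 | 0 |
| 70% | −0.2 | −0.5 | −0.8 |

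**5. Scale.** For 80 and 40 completers (the 40 assumes 40% retention of 100), SE = SD × √(1/80 + 1/40). Assumed SDs of 12, 15 and 18 give 2.3, 2.9 and 3.5 points. This is a completers-only approximation, not the MMRM standard error.

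**6. What each planned analysis does about missed visits.**

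| Analysis | Handling |
|---|---|
| Main MMRM, per protocol MMRM | MAR |
| Plots (16.1.1.2) | None; observed means only |
| ANCOVA at LOCF endpoint | Last score held fixed |
| Complete-case MMRM | Leavers dropped |
| Item imputation | MAR; wholly missed assessments stay missing |

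LOCF and the complete-case analysis use other assumptions than the main model. Each is a single fixed one, and no row gives a graded departure from MAR.

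**The case against.** The strongest reply is that this is a safety study with an exploratory efficacy part. The primary endpoint is adverse event incidence, Protocol 4.4 states no efficacy hypothesis, and SAP 7.4 reports nominal p-values. There is no efficacy success criterion, only the general rule in SAP 6.6: "The default significance level will be 5%; confidence intervals (CIs) will be 95%; and all p-values will be two-sided". The protocol's wording on departures from MAR is permissive. All of this stands and limits the weight of the point.

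Second, the LOCF ANCOVA and complete-case MMRM cover both endpoints. A reader of 16.1.1.2 alone might infer that MAR goes untested. That is too strong, because the next section offers two contrasts with it. They remain weak checks, since agreement or disagreement with them does not show how large a departure would alter the result.

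Third, leaving for lack of efficacy does not by itself violate MAR. Missingness may depend on observed scores, and PANSS and CGI-S are scheduled at the ET visit, so worsening before exit will often be in the model. Relapse (which counts discontinuation for exacerbation) and time to discontinuation are also analysed. This is fair: MAR may be adequate. The plan simply gives no way to judge how much depends on it.

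Fourth, SAP Appendix 3 is redacted, and SAP Section 20 lists two pattern-mixture implementation papers that no visible text cites. Such an analysis may exist there. But 16.1.1.2 is not redacted and points to none.

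**Conclusion.** The point holds as an inexpensive improvement to an exploratory analysis. The section headed as sensitivity analyses is descriptive for both PANSS total and CGI-S, and no visible SAP text specifies a formal missing-not-at-random analysis for Week 52.

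On an assumed 5-point departure, the SEP-363856 mean moves by about 3.0 points, or 2.8 to 2.9 with ET scores mapped forward. That is similar to the approximate standard error of the difference, 2.3 to 3.5 points on assumed SDs. If both arms depart equally, the difference moves by only +1.0 to -0.5 points for assumed quetiapine XR dropout of 40% to 70%. Each arm's own mean still moves in proportion to its missing fraction.

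Three stronger readings are not supported:
- A reader might infer that 60% of SEP-363856 PANSS data will be missing. The 60% is subjects not completing to Week 52. Earlier visits are observed, and average missingness is about 22% to 42% under the assumed shapes.
- A reader might infer that the SAP breaks a protocol commitment. Protocol 15.3.5 only permits the analysis.
- A reader might infer that the treatment difference is off by 3 points. That needs the departure to occur in SEP-363856 alone, and the documents give no size for it in either arm.

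**What to change.** Add to SAP 16.1.1.2 a delta-adjusted multiple imputation for Week 52 PANSS total and CGI-S:
- Impute missed visits under MAR within arm, then add delta to post-dropout values. Set the range and steps of delta in advance, separately for each scale.
- Apply delta in SEP-363856 alone, then in both arms.
- Across delta, report the arm means, the difference and its 95% CI, and the delta (if any) at which the nominal CI changes its relation to zero.
- Keep the plots and call them descriptive.

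If Appendix 3 already holds such an analysis, 16.1.1.2 should point to it. If the sponsor decides against one, the minimum is to record in SAP 3.7 that the optional protocol analysis is not planned and to label the Week 52 MMRM as dependent on MAR.

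The cost is a SAP paragraph and standard multiple imputation code. The SAP already plans imputation with pooled results for partly completed PANSS assessments, so the method is not new to the study. The downside is modest programming and an exploratory Week 52 result that may look less certain.

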16.1.1.3. Supplementary Analyses of PANSS Total Score

- Analysis of covariance

Change from Baseline in PANSS total score at each scheduled visit and at the LOCF endpoint will be analyzed using an analysis of covariance (ANCOVA) model. The model will include factors for treatment and country, and include Baseline PANSS total score as a covariate. The LS mean of each treatment group, LS mean differences (SEP-383656 vs. Quetiapine), their standard errors and two-sided 95% CIs, and the nominal p-values for treatment differences will be obtained from the model.

Based on the ANCOVA analysis, within group effect size at a given time point will be calculated as the LS mean of the treatment group divided by the standard deviation, obtained as the standard error of the LS mean multiplied by the square root of the treatment group sample size at that time point. Between group

Document: CCI

Author: PPD

Version Number: 0.6

Version Date: 30JAN2023

Template No.: CS_TP_BS016 Revision 6

Reference: CS_WI_BS005

Effective Date: 02Dec2019

effect size at a given time point will be calculated as the LS mean difference of SEP-363856 vs. Quetiapine divided by the pooled standard deviation, obtained as the standard error of the LS mean difference divided by the square root of the sum of inverse treatment group sample sizes at that time point.

Baseline PANSS total score will also be analyzed by an ANCOVA model including factors for treatment and country. The nominal p-values for treatment differences will be obtained from the model.

- Complete case analysis

The complete case analysis will be performed on the subset of subjects in the efficacy population who completed the double-blind treatment period and have Week 52/Visit 17 PANSS total score data available within 9 days post the last dose. The MMRM analysis as described in [Section 16.1.1.1](#) will be performed on these subjects.

- Analysis on the PP population

The MMRM analysis as described in [Section 16.1.1.1](#) will be performed on the PP population to evaluate the efficacy of the treatment for these subjects.

- Analysis with missing PANSS item(s) imputed

Due to the use of electronic clinical outcome assessment (eCOA) technology and extensive data quality monitoring during the study, no partially completed PANSS assessments are expected. However, in the rare event of a partially completed PANSS assessment, missing PANSS item scores will be imputed as described below.

In contrast to all other analyses of the efficacy variable where missing PANSS item scores are not imputed and the corresponding PANSS total score is set to missing, in this supplementary analysis, if a PANSS assessment is partially available at a visit (i.e. one or more PANSS items are missing), the missing PANSS item(s) will be imputed. It should be noted that entirely missing PANSS assessments will not be filled in using imputation in this analysis.

The Markov Chain Monte Carlo (MCMC) method is used to obtain full datasets. Under the assumption that each PANSS item X score and dichotomized countries have a multivariate normal distribution, the MCMC method is used to impute missing values assuming MAR (using the SAS MI procedure with the MCMC statement and the IMPUTE=FULL option), by using a data augmentation algorithm, with each

Document: CCI

Author: PPD

Version Number: 0.6

Version Date: 30JAN2023

Template No.: CS_TP_BS016 Revision 6

Reference: CS_WI_BS005

Effective Date: 02Dec2019

iteration n consisting of an imputation step and a posterior step. The imputation step uses a random draw of $\theta^{(n)}$, parameter of the joint imputation model, to sample missing values from a conditional distribution $P(Y_{mis}|x, y_{obs}, \theta^{(n)})$, obtaining $y_{mis}^{(n)}$, the subset of missing values that need to be filled in to obtain full datasets. The posterior step simulates a new draw of the parameter $\theta^{(n+1)}$ from the posterior distribution given the current full data $P(\theta|x, y_{obs}, y_{mis}^{(n)})$ with a non-informative Jeffreys prior. Treatment group will be taken into account for this imputation (i.e., missing data will be imputed for each treatment group separately). These steps are repeated to obtain 1000 full datasets. The random seed number is specified in the sample SAS code ([APPENDIX 3](#)).

For each PANSS item X that needs such imputation, MCMC imputation will be performed based on a multivariate normal distribution including variables for dichotomized countries, Baseline PANSS item X score, and all post-Baseline PANSS item X scores (Week 1/Visit 3, Week 4/Visit 5, Week 8/Visit 6, Week 16/Visit 8, Week 24/Visit 10, Week 32/Visit 12, Week 40/Visit 14, Week 48/Visit 16, Week 52/Visit 17). The imputation will be done by treatment group. By using this method, those visits where entire PANSS assessments are missing will have item X filled in as well. When calculating PANSS total scores on the imputed datasets, the imputed values for those visits should be ignored.

A total of 1000 imputed datasets will be generated for each PANSS item to be imputed this way. Upon completion of the imputation for all individual PANSS items, the datasets for each PANSS item will be combined by the imputation number. PANSS total scores will be calculated for the visits where PANSS assessments are completely or partially available in the original data, using observed/imputed PANSS item scores. As stated earlier, for visits where PANSS assessments are entirely missing in the original data, the PANSS total score should be left as missing.

Each of the 1000 imputed datasets with PANSS total score calculated will be analyzed using the MMRM analysis as described in [Section 16.1.1.1](#). Results from the analysis of each imputed dataset, i.e., the LS means of each treatment group, the LS mean treatment differences (vs. Quetiapine XR), and their standard errors, will be combined using Rubin's imputation rules to produce pooled LS mean and LS mean difference estimates, their standard errors and 95% CIs, and pooled p-values.

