3.4. DETERMINATION OF SAMPLE SIZE

A total of 300 subjects are expected to be enrolled from approximately 50 global sites, including the US and Europe. Subjects will be assigned randomly to receive SEP-363856 or active comparator in an allocation ratio of 2:1. The determination of sample size was based upon clinical considerations. The sample size of 300 subjects will provide approximately 80 subjects who are expected to complete 1 year

Document: CCI

Author: PPD

Version Number: 0.6

Version Date: 30JAN2023

Template No.: CS_TP_BS016 Revision 6

Reference: CS_WI_BS005

Effective Date: 02Dec2019

of treatment with SEP-363856 to support sufficient long-term safety data on SEP-363856.

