16.1.1. OBSERVED VALUES AND CHANGE FROM BASELINE IN PANSS TOTAL SCORE

16.1.1.1. Exploratory Analysis of PANSS Total Score

Data will be analyzed using a mixed model for repeated measures (MMRM) under the MAR assumption. Under this assumption, the efficacy outcome of subjects in each treatment group after early discontinuation will exhibit the same future evolution as subjects in the same group remaining in the study. The MMRM model will include fixed factors for treatment, visit (Weeks 1, 4, 8, 16, 24, 32, 40, 48, 52; as a categorical variable), country, and treatment-by-visit interaction and include Baseline PANSS total score as a covariate. An unstructured covariance matrix will be used to model the within-subject correlation. Kenward-Roger approximation will be used to calculate the denominator degrees of freedom.

The least squares (LS) mean difference in PANSS total score change from Baseline at Week 52 (SEP-363856 group vs. Quetiapine), their standard errors, the two-sided 95% CIs, and the associated nominal p-values will be calculated from the MMRM model.

In addition, the following statistics will be reported in the MMRM table:

Document: CCI

Author: PPD

Version Number: 0.6

Version Date: 30JAN2023

Template No.: CS_TP_BS016 Revision 6

Reference: CS_WI_BS005

Effective Date: 02Dec2019

- The LS mean difference in PANSS total score change from Baseline at Weeks 1, 4, 8, 16, 24, 32, 40, 48; their standard errors; the two-sided 95% CIs; and the associated nominal p-values.
- The LS mean of PANSS total score change from Baseline at each time point for each treatment group, their standard errors, and the two-sided 95% CIs.
- Within group effect size at each time point, calculated as the LS mean of each treatment group at each time point divided by the model estimate of standard deviation, obtained as the square root of the corresponding diagonal element of the residual covariance matrix (R matrix from PROC MIXED).
- Between group effect size vs. Quetiapine at each time point, calculated as the LS mean difference of each SEP-363856 group vs. Quetiapine at each time point divided by the model estimate of standard deviation, obtained as the square root of the corresponding diagonal element of the residual covariance matrix (R matrix from PROC MIXED).

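### The within-group ANCOVA effect size divides by SE(LS mean) × √n, which overstates the residual SD when countries differ in size (if LS means weight countries equally), more so in the SEP-363856 arm

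*SAP*

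**What the plan says.** SAP section 16.1.1.3 (analysis of covariance) analyses change from Baseline in PANSS total score at each scheduled visit and at the LOCF endpoint. On the model it says: "The model will include factors for treatment and country, and include Baseline PANSS total score as a covariate". The within-group effect size is the arm's LS mean over an SD that is "obtained as the standard error of the LS mean multiplied by the square root of the treatment group sample size", with n counted at the visit in question. The between-group effect size uses a pooled SD "obtained as the standard error of the LS mean difference divided by the square root of the sum of inverse treatment group sample sizes".

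For the MMRM, section 16.1.1.1 takes the SD for both effect sizes directly from the model: it is "obtained as the square root of the corresponding diagonal element of the residual covariance matrix".

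Sections 7.1 and 7.2 name four countries: the United States, Russia, Romania and Ukraine. Section 3.2 stratifies randomization by country. Neither document gives expected or capped enrolment by country. The visible SAP does not say how LS means weight the countries, and the sample code in Appendix 3 is redacted.

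The same ANCOVA is called for the PANSS subscale, Marder and UPSM scores (sections 16.1.2 to 16.1.5) and for CGI-S, BNSS, MADRS, BACS, ESS, SLOF, EQ-5D-5L VAS and index, UPSA-B and MSQ (sections 16.2.1 to 16.2.9).

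**The concern.** Multiplying a standard error by √n returns the SD for a simple arm mean, whose variance is σ²/n. An LS mean from a model with a country factor is a different quantity. It predicts the arm's mean at a chosen country mix, and its variance includes a term for the distance between that mix and the mix actually enrolled. Under the usual equal weighting, a small country has the same influence as a large one, and the standard error rises accordingly. The SAP's rule turns that extra uncertainty into an apparently larger SD.

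Two arms with the same true standardized change could then show different within-group effect sizes only because allocation is 2:1. The divisor would also vary between visits if dropout changed the country mix. For EQ-5D-5L and MSQ, and for every LOCF endpoint, no MMRM effect size is planned that could reveal the problem.

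**Working it through.** The plan states no numerical SD or effect size, so there is no figure to reproduce. The formula itself is tested.

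**Inputs**
- Allocation, SAP section 3.4: "Subjects will be assigned randomly to receive SEP-363856 or active comparator in an allocation ratio of 2:1". The arm shares are p = 2/3 (SEP-363856) and p = 1/3 (quetiapine XR).
- Planned size, SAP section 3.4: "A total of 300 subjects are expected to be enrolled from approximately 50 global sites". This gives N = 300, that is 200 and 100.
- K = 4 countries (SAP sections 7.1 and 7.2).
- Assumption: LS means weight the four countries equally.
- Assumption: the 2:1 ratio holds within each country, as stratification intends.
- Assumption: the country shares w_c, because the documents give none.

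**Step 1. Variance of the LS mean.** In an ANCOVA, the adjusted mean of arm t at target point x* has variance σ² × [1/n_t + (x* − x̄_t)′ S⁻¹ (x* − x̄_t)], where x̄_t is the arm's own mean of the country indicators and Baseline, and S is the pooled within-arm cross-product matrix. The second term cannot be negative, so SE × √n_t is never below σ.

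**Step 2. The country term.** With equal weights as the target and the same country mix in both arms, the second term is (H − 1)/N, where H = (1/16) × Σ(1/w_c). Multiplying the variance by n_t = p × N gives

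implied SD = σ × √[1 + p(H − 1)].

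H equals 1 only when all four shares are 25%. The excess is proportional to p, so it is larger in the two-thirds arm.

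**Step 3. Numbers**
- 25/25/25/25: Σ(1/w) = 16, H = 1.00. Both factors are 1.00.
- 40/30/20/10: Σ(1/w) = 2.50 + 3.33 + 5.00 + 10.00 = 20.83, H = 1.302. SEP-363856 √(1 + 0.201) = 1.10; quetiapine XR √(1 + 0.101) = 1.05.
- 50/30/15/5: Σ(1/w) = 2.00 + 3.33 + 6.67 + 20.00 = 32.00, H = 2.00. SEP-363856 √1.667 = 1.29; quetiapine XR √1.333 = 1.15.
- 60/25/12/3: Σ(1/w) = 1.67 + 4.00 + 8.33 + 33.33 = 47.33, H = 2.958. SEP-363856 √2.306 = 1.52; quetiapine XR √1.653 = 1.29.

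**Step 4. Effect on a true within-group effect size of 0.80 in both arms** (0.80 divided by the factor)

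| Assumed country mix (%) | SEP-363856 | Quetiapine XR |
|---|---|---|
| 25/25/25/25 | 0.80 | 0.80 |
| 40/30/20/10 | 0.73 | 0.76 |
| 50/30/15/5 | 0.62 | 0.69 |
| 60/25/12/3 | 0.53 | 0.62 |

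**Step 5. Checks**
- Exact matrix calculation, L(X′X)⁻¹L′, agreed with the closed form to three decimals wherever 2:1 held in every country. At 40/30/20/10 and N = 300 it gave 1.096 and 1.049.
- Adding the Baseline covariate changed these to 1.097 and 1.051, which is negligible.
- At N = 120 (80 and 40, assuming equal retention) the same mix gave 1.098 and 1.052. The problem depends on country shares, not on total size.
- In 3,000 random four-country designs the factor never fell below 1.000.
- Weighting LS means by observed country shares brought the factor back to about 1.00 in both arms.
- Between-group formula: with 2:1 in each country, the difference has variance σ²(1/n₁ + 1/n₂), so the SAP's division recovers σ. With the Baseline covariate the ratio was 1.001 to 1.009 in all scenarios.

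**The case against.** The strongest objection is that equal weighting is not written down. Equal weighting is the usual SAS default, but the code appendix cannot be read, and under observed-margins weighting the rule works. This stands as a limit: the finding is conditional, and the text should settle it either way.

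A second objection is that the magnitudes rest on invented country shares. That also stands. The range starts at no error, and nothing in the documents says where in it the trial falls. The SAP does allow for very small cells: section 16.1.1.4 drops subgroups, country among them, with fewer than two Week 52 subjects in either arm.

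A third objection is consequence. The section is supplementary, Protocol section 15.3.5 calls all efficacy analyses exploratory, and no planned decision uses a within-group effect size. The distortion shrinks the test drug more than the comparator, so it does not flatter SEP-363856. All of this holds and limits the weight of the point.

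A reader might infer that the ANCOVA and MMRM effect-size tables would agree but for this rule. The documents do not support that. EQ-5D-5L, MSQ and the LOCF endpoints have no MMRM counterpart. Where both models are run, a per-visit ANCOVA and a repeated-measures model can differ in both LS means and residual SDs. A reader might also infer that the comparison between arms is biased. It is not, because the between-group formula is essentially correct.

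**Conclusion.** The concern holds in a limited form. As written, the rule does not in general return the quantity it calls a standard deviation. Given equal-weight LS means, the direction is certain: the SD is overstated whenever countries differ in size, and more in the SEP-363856 arm. The size is unknown and runs, over the assumed mixes, from no inflation to 52% (SEP-363856) and 29% (quetiapine XR). More extreme mixes would go further.

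The error is confined to the within-group ANCOVA effect sizes, for PANSS total score and the scales that refer to section 16.1.1.3. LS means, standard errors, confidence intervals and p-values are unaffected. It is worth correcting because the printed numbers would be mislabelled and not comparable between arms, but it does not touch the trial's primary safety conclusions.

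**What to change.** In SAP section 16.1.1.3, define the within-group divisor as the root mean square error of the ANCOVA at that time point. This follows the residual-SD approach of section 16.1.1.1 and gives a factor of 1.00 in both arms whatever the country mix. The between-group formula can stay as written.

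If observed-margins LS means were intended, stating that would also repair the within-group rule, but it would change the LS means being reported. The root mean square error is the smaller change.

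The cost is one sentence in the SAP and one line of code, with no new data and no effect on any test or interval.
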